# Promoting Asylum-seeking and Refugee Children's Coping With Trauma

## Background and Status of Knowledge

Mental health problems and disorders represent major risks for unsuccessful integration into societies' productive institutions, and account for more than half of the health expenses [1]. Moreover, mental health problems increase the risk for social exclusion, peer rejection [2], and school drop-out [3] and is thereby a substantial barrier to social integration of refugees. Research among unaccompanied minor asylum-seekers awaiting a decision on their application for asylum has demonstrated prevalence of symptoms of post-traumatic stress disorder (PTSD) from 54% to 76% [4, 5]. Furthermore, there is high stability of mental health problems and disorders among them after they receive residence [6, 7]. Improving the mental health of this vulnerable group of children may improve the life conditions and opportunities for the children themselves, and can thereby be economically beneficial to the receiving societies.

There is general agreement in the literature that Trauma-Focused Cognitive Behavioral Therapy (TF-CBT) is the method of choice for treating PTSD in trauma-exposed children [8]. Nevertheless, health personnel and national health authorities have pointed to the existing challenges regarding both capacity and competence in mental health specialist services to meet the mental health needs of asylum-seekers and refugees [9-11]. In response to the resulting socio-cultural differences in mental health services, commissioned by three directorates, the Norwegian Institute of Public Health (NIPH) has recently implemented a low-threshold evidence based intervention (Teaching Recovery Techniques) to reduce trauma-related mental health problems and promote well-being among asylum-seeking and refugee minors. The overall aim of the proposed PhD project is to evaluate the effectiveness of the intervention, which was delivered by local environmental therapists, school personnel, and health nurses to UMA and URM. The PhD project is based on data that we collected in conjunction with the intervention; consequently, funding of the project will facilitate an immediate generation of new and important knowledge.

## Mental health, trauma and psychosocial stressors

The World Health Organization (WHO) defines mental health as a state of well-being in which every individual realizes his or her own potential, can cope with the normal stresses of life, can work productively and fruitfully, and is able to make a contribution to her or his community [12]. In its most recent Strategy of good mental health [13], the Government describes mental health as including good mental health, quality of life, mental health problems and mental health disorders. Quality of life (QoL) involves a range of different positive experiences such as happiness, safety, affiliation, coping, and meaningfulness (p. 9),

---

 *Unaccompanied minor asylum-seekers* (UMA) are children below 18 years of age, who travel without the company of an adult legal caretaker to seek asylum in a foreign country. We distinguish this group from *unaccompanied refugee minors* (URM), who are former UMAs that have been granted asylum and are resettled in municipalities. We refer to them as refugees even if protection was conceded for humanitarian or other reasons rather than to shield from persecution, imprisonment etc.

and is conceptualized in a variety of ways [14]. In the present study, QoL refers to perceived subjective wellbeing and self-efficacy.

UMA and URM all have in common that they have experienced serious losses of or separation from parents and other family members. Additionally, a majority of them have been exposed to an accumulation of traumatic events before their arrival in the destination countries, when they feared for their own lives or for the lives of others [15, 16]. Many children demonstrate adaptive outcomes in spite of the amount of adversities they are exposed to [17, 18]. Nevertheless, war trauma increase the risk of symptoms of PTSD and other mental health problems among asylum-seeking and refugee children and youth [6, 19, 20]. Likewise, war-trauma may be associated with post-traumatic growth in some individuals [21], however, reduced QoL is frequently the outcome [22]. Furthermore, research with older refugees and war-affected populations has shown that asylum-related and post-resettlement psychosocial stressors experienced after residence has been obtained, contribute to the maintenance and development of mental health problems [23-26] and decreased QoL [14, 22]. In Norway, as in Sweden, new and more restrictive immigration policies implemented in response to the unprecedented high numbers of asylum-seekers arriving in 2015 resulted in alarming increases in suicide attempts, self-harm, school-drop out, withdrawal, apathy, and flights among the UMA [27, 28]. However, we lack more specific information about the mental health reactions to the combined impact of traumatic events and asylum-stressors among UMA and URM. Such information may inform about the strengths and vulnerabilities of these children. Moreover, experiences of a substantial number of asylum-related and post-resettlement psychosocial stressors provide a challenging context for the implementation of the intervention we are studying that may interfere with its effectiveness.

## Teaching Recovery Techniques: An Effective Short-term Intervention

Teaching Recovery Techniques (TRT) is a manualized, short term, group based intervention, which specifically focuses on children's symptoms of PTSD. TRT was developed by experts of the Children and War Foundation (C&W; [www.childrenandwar.org](http://www.childrenandwar.org)) to heal children's mental reactions to war and disaster-related trauma [29]. The aim of the intervention is to teach children self- help methods, by increasing perceptions of control and self-efficacy in relation to trauma symptoms, based on recommended and evidence based CBT- methods for trauma relief. The five sessions help students to understand the causes of trauma and recognize signs and symptoms. Adolescents are taught a range of coping skills to stop flashbacks and other intrusive images, sounds, or smells. Student hyperarousal is addressed through stabilization and relaxation techniques, and phobic avoidance behavior is gradually desensitized through use of relaxation with anxiety and anger hierarchies.

The program is delivered to groups of 5 - 15 adolescents by local group-leaders in pairs that are trained by representatives from C&W.

TRT has proven to be effective in reducing trauma-related mental health symptoms in contexts of war and disaster when delivered by non-clinicians and "lay" people [30-35]. However, TRT has rarely been implemented with UMA or URM in post-war contexts, who have a longer time span since the traumatic exposure than children in contexts of war, and who are experiencing additional psychosocial challenges. A small study conducted in the

U.K., showed more beneficial mental health effects among refugees than asylum-seekers, and the authors speculated if experiences of post-migration stressors might have reduced the effectiveness in the latter group [36]. A small pilot study in Sweden yielded positive effects of TRT among 48 UMA and URM.

In spite of the focus of TRT to increase coping and self-efficacy, none of the above mentioned studies included any measures of QoL-related constructs. To enhance our knowledge of the effectiveness of TRT in post-war contexts, we expand on the designs of the referred studies by 1) including a wait-list control group; 2) examining longer term effects; 3) including QoL-related outcomes (subjective wellbeing and self-efficacy) in addition to symptoms of PTSD, and 4) taking the psychosocial context into consideration.

## Aims

The overall aim is to evaluate the effectiveness on mental health of TRT among unaccompanied minor asylum-seekers and refugees.

More specifically, we will:

Examine the short and long-term effectiveness of TRT in reducing mental health symptoms and promote QoL

- *Primary hypothesis:* The TRT intervention is expected to significantly improve the mental health status (i.e. alleviate symptoms of post-traumatic stress disorder, depression and anxiety and promote QoL) compared to the waiting-list control group.
- *Secondary hypotheses:* 1) Asylum- related and post-resettlement psychosocial stressors predict mental health problems and QoL over and above pre-migration traumatic exposure. 2) Asylum-related and post-resettlement psychosocial stressors predict variation in the short and long term effects of the effect of the TRT.

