### Sample

The study involves about 170 UMA and URM  $> 8$  years.

Recruitment involved inviting reception centers and municipalities from all over Norway to participate as a first step. The children in the centers and municipalities that accepted to participate who spoke Pashto, Dari, Arabic, Somali or Tigrinya, were then invited to

participate (see information below).

A total of 18 TRT-groups have been conducted during the project period. To avoid cross-contamination [37] of the intervention, the children were allocated to Intervention or Control groups on an institutional level. We endorsed half of the participating reception centers and resettlement municipalities to Intervention Groups, and the other half to wait-list Control Groups. We did this based on practical considerations related to the data collection, such as time frames of the commission, geographical location of the targeted centers and municipalities, and availability of bilingual research assistants. The Intervention Groups started the TRT soon after the information meeting, and the Control Groups started when they had completed the five weekly sessions and the W2 data collection.

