### **Procedures**

Treatment response was registered by self-report questionnaires administered before upstart of TRT (W1), two weeks after the completion of TRT (W2) and two months after completion of TRT (W3). The questionnaires were translated to the participants' respective languages by standardized back-translation procedures. The children filled in the questionnaires in a group setting. The trained bilingual research assistants read the questions to the children, and assisted them with language issues.

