### Mental Health Outcomes

**Symptoms of PTSD:** Children's Revised Impact of Event Scale, CRIES-8 (31, 39) with eight items of intrusion and avoidance was used for screening purposes, and CRIES-13 (42) with additional five hyperarousal items was used at W1, W2 and W3 [30, 39].

**Qualitive of Life:** 1) **Subjective Well-being:** Cantril Ladder [40]. The participants are presented with an illustration of a ladder with ten steps, and informed that the best possible life for them being on step 10, and the worst possible life being a 0. 2) **Perceived Self-Efficacy:** was measured by a short version of five items of The Generalized Self-Efficacy scale, GSE [41] that has previously been used with immigrant populations in Norway [42].

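### The aims refer to long-term effectiveness and long-term moderation, but the last assessment is two months after TRT and no untreated comparison is planned at that point

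*Combined protocol and SAP*

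**What the plan says.** The first aim is to "Examine the short and long-term effectiveness of TRT in reducing mental health symptoms and promote QoL". Secondary hypothesis 2, in the same section, says that asylum-related and post-resettlement stressors "predict variation in the short and long term effects of the effect of the TRT". The primary hypothesis names the comparator: improvement is judged "compared to the waiting-list control group".

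The Procedures section gives three waves: W1 before TRT starts, then "two weeks after the completion of TRT (W2) and two months after completion of TRT (W3"). The Mental Health Outcomes section agrees for the PTSD measure, where CRIES-13 with its "additional five hyperarousal items was used at W1, W2 and W3". No later assessment is described anywhere, and long-term is not defined.

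On the wait-list, the Sample section says that "the Control Groups started when they had completed the five weekly sessions and the W2 data collection". In context, the completed sessions are those of the Intervention Groups.

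**The concern.** An aim fixes what a trial may conclude. This one promises a short-term and a long-term answer, and W3 is the only wave that could carry the long-term part. Two features of W3 stand in the way.

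- **Timing.** W3 comes only weeks after W2, so the two waves describe nearly the same period after treatment.
- **Comparator.** The primary hypothesis rests on comparison with the wait-list, but the wait-list groups are due to begin TRT after W2. A group difference at W3 would no longer compare TRT with no TRT.

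If the plan is followed as written, a two-month result without an untreated comparator could be labelled long-term effectiveness. The same holds for secondary hypothesis 2: an association between stressors and outcome at W3 could be labelled moderation of a long-term effect that the design does not estimate.

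**Working it through.** The plan gives no figure of its own to reproduce here. Its sample size and power statements are not tied to W2 or W3 and do not enter the argument. The check is calendar arithmetic on the stated schedule.

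**Inputs**
- W2: 2 weeks after completion of TRT (Procedures).
- W3: 2 months after completion of TRT (Procedures).
- TRT: five weekly sessions (Sample), spanning 4 weeks from first to last session, or 5 weeks if counted as full weeks.
- Controls start TRT after the W2 data collection (Sample). The lag is not stated.

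**Step 1: interval from W2 to W3.** Interval = 2 × (weeks per month) − 2.

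| Month taken as | W3 after completion (weeks) | W3 − W2 (weeks) |
|---|---|---|
| 4 weeks | 8.0 | 6.0 |
| 30 days (4.29 weeks) | 8.57 | 6.57 |
| 365.25/12 days (4.35 weeks) | 8.70 | 6.70 |

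The short-term and supposedly long-term assessments are therefore 6.0 to 6.7 weeks apart.

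**Step 2: position in the intervention groups, counted from their first session.**
- W2 is at 4 + 2 = 6 to 5 + 2 = 7 weeks.
- W3 is at 4 + 8.0 = 12.0 to 5 + 8.7 = 13.7 weeks.

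**Step 3: status of the controls at that W3.** Assume first that controls start immediately after W2.
- With a 4-week span, they finish at 6 + 4 = 10 weeks, against W3 at 12.0 to 12.7 weeks. They finish 2.0 to 2.7 weeks before it.
- With a 5-week span, they finish at 7 + 5 = 12 weeks, against W3 at 13.0 to 13.7 weeks. They finish 1.0 to 1.7 weeks before it.

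The contrast at W3 is then treated against treated. With a delayed start, controls would be part-way through TRT at W3. They would still be untreated only if the start slipped by more than the whole W2 to W3 interval, 6.0 to 6.7 weeks. The plan provides for no such delay.

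**Step 4: the other reading of W3 for controls.** Procedures dates W3 from completion of TRT. If that means each group's own TRT, the controls' W3 is by definition after treatment and is not concurrent with the intervention groups' W3. Neither reading plans an untreated comparison at W3.

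**Step 5: what each wave can carry.**

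| Wave | Untreated wait-list comparison planned? | Supportable statement |
|---|---|---|
| W2 | Yes, if controls are assessed before they start TRT | Short-term effect against the wait-list |
| W3 | No | Whether the W2 result is still present two months after TRT |
| Later | No observation | None |

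**The case against.** **Long-term is only a label.** The term is undefined, Procedures states all three waves openly, and a reader can map short to W2 and long to W3. This stands in part: the documents set no threshold, so calling two months too short is a judgement. It does not rescue the aim, because the lack of an untreated comparison at W3 does not depend on the label.

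**The mixed models use all waves.** The Statistical Analyses section names ANCOVA and mixed regression models. These can describe W3, but they do not create an untreated group there, and the section does not say how the controls' own TRT after W2 would enter. If TRT works, a plain group difference at W3 would tend to understate its effect. A within-group change would include whatever natural course occurred.

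**Stronger readings that the documents do not support**
- *A reader might infer that the trial cannot show benefit lasting into resettlement.* The Background does say that "there is high stability of mental health problems and disorders among them after they receive residence", but this describes persistence and sets no follow-up horizon. The sample includes unaccompanied refugee minors, whom the protocol defines as already resettled, so for them every wave falls within resettlement.
- *A reader might fault the TRT section's claim of "examining longer term effects" on the same ground.* That wording is comparative with earlier studies whose follow-up lengths the documents do not give. It may be accurate and cannot be checked here.
- *A reader might take 12 to 14 weeks as the whole observation span for every child.* Those figures run from the first session in the intervention groups. The lag from W1 to the first session is not stated, and the controls' span depends on which reading of W3 applies.
- *A reader might infer that W3 will be presented to directorates as long-term benefit.* The section on implementing findings describes audiences and channels only, and says nothing about how W3 will be described.

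**Conclusion.** The concern holds for the aim and for secondary hypothesis 2. Both state a property that the design does not have. Observation after TRT stops at two months, W3 is 6.0 to 6.7 weeks after W2, and no untreated comparison is planned at W3. What remains is a wait-list comparison at W2 and a description of maintenance to two months.

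The conclusion rests on two assumptions: that W3 is the last wave, since none later is described, and that controls began TRT after W2 as the Sample section says. The statement about W2 further assumes that controls were assessed at W2 before starting TRT. That comparison is with a concurrent wait-list allocated by institution on practical grounds, and this point does not judge the allocation.

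Severity is low. The defect lies in what is claimed and does not invalidate the data or the W2 comparison.

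**What to change.** 1. In the aim and in secondary hypothesis 2, replace long-term with two-month follow-up.
2. State that conclusions on durability are limited to two months after completion of TRT.
3. Report W3 as maintenance of the W2 result, not as a long-term effect against the wait-list. Report any association with stressors at W3 as relating to the two-month follow-up, not as moderation of a long-term effect.

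The claim of longer-term effects in the TRT section need not change on this account.

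The Progress Plan lists data collection as completed, with analysis and five articles still to come, so the wording can be settled before those articles are written. The change touches no visit, sample or collected data. Its cost is a less favourable stated claim.

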### Power

Several power analyses have been performed to calculate the required sample size, given an  $\alpha$ -level of 0.05 and power ( $1-\beta$ ) of 0.80. The analyses show that a sample of  $n=150$  will be sufficient to detect standardized regression effects of 0.20 or larger. For intervention effects there will be power to detect effect sizes of  $d=0.40$  or larger. With use of linear mixed effect models and structural equation modelling, and the wait-list design, power will be even higher. Thus, we are confident that the planned sample size is sufficient to address the research questions posed.

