### Statistical Analyses

Treatment effects will be analyzed using ANCOVA and mixed regression models that may be flexibly adjusted according to the dependency structure in the repeated data.

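### The primary hypothesis spans PTSD, depression, anxiety and QoL without naming a primary outcome, a primary wave or a rule for combining results, and depression and anxiety have no named measure in this document

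*Combined protocol and SAP*

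**What the plan says.** All references are to the combined protocol and SAP.

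- **Aims.** There is one primary hypothesis: TRT will improve mental health status, spelled out as "alleviate symptoms of post-traumatic stress disorder, depression and anxiety and promote QoL", "compared to the waiting-list control group". None of the four components is ranked above another.
- **Mental Health Outcomes.** For PTSD, CRIES-8 is the screening tool and "CRIES-13 (42) with additional five hyperarousal items was used at W1, W2 and W3". QoL has two measures: the Cantril Ladder for well-being, and self-efficacy, which "was measured by a short version of five items of The Generalized Self-Efficacy scale, GSE". No depression or anxiety scale appears. The list of design extensions at the end of the section on Teaching Recovery Techniques likewise gives only QoL-related outcomes and PTSD symptoms.
- **Power.** Alpha of 0.05 and power of 0.80 are inputs, and n=150 is said to detect d=0.40. Neither the outcome nor the sidedness is given. The section adds: "With use of linear mixed effect models and structural equation modelling, and the wait-list design, power will be even higher".
- **Statistical Analyses.** The section is a single sentence: "Treatment effects will be analyzed using ANCOVA and mixed regression models", adaptable to the dependency in the repeated data. It names no outcome, wave, composite, hierarchy or multiplicity rule.
- **Sample and Procedures.** Assessments are at W1 (before TRT), W2 (two weeks after) and W3 (two months after), and "the Control Groups started when they had completed the five weekly sessions and the W2 data collection". W2 is thus the last wave with untreated controls, but it is not labelled primary.

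**The concern.** A primary hypothesis needs a rule saying which results confirm it. Here at least three rules fit the text: improvement on any listed outcome, improvement on all of them, or improvement on one overall construct. They have different error rates and different power, and the same data could confirm the hypothesis under one and fail to confirm it under another. The Progress Plan shows data collection finished, with analysis and five articles to follow, so the choice could be made after results are known.

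Separately, two of the four components of the hypothesis have no stated measure. As written, this document gives no means of testing them.

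**Working it through.** **1. The plan's own figure.** With 75 per arm (n=150 split equally, as half the institutions went to each arm) and d=0.40, power = Φ(d·√(n/2) − z), where n is the number per arm and d·√(75/2) = 2.449.
- Two-sided 0.05: Φ(2.449 − 1.960) = 0.688.
- One-sided 0.05: Φ(2.449 − 1.645) = 0.789.
- Two-sided ANCOVA with an assumed baseline–outcome correlation of 0.5: Φ(2.449/√0.75 − 1.960) = 0.807.

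The stated 0.80 is therefore reachable for one outcome, but only with an assumption the plan does not state. It makes no allowance for several outcomes or for clustering.

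**2. Inputs for the comparison of readings.**
- Three outcomes at W2: CRIES-13, Cantril Ladder, GSE (from Mental Health Outcomes).
- Each tested two-sided at 0.05 (0.05 from Power; sidedness assumed).
- Normal test statistics with a common pairwise correlation ρ from 0 to 0.7 (assumed; the document gives none).
- Each test has power 0.80 when taken alone (granted for illustration).

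**3. Formulas at ρ = 0.**
- Any one suffices, either direction: 1 − 0.95³ = 0.143.
- Any one suffices, favouring TRT: 1 − 0.975³ = 0.073.
- All three must succeed: 0.80³ = 0.512.
- Power needed per test for a joint 0.80: 0.80^(1/3) = 0.928.

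For ρ > 0 the same quantities come from numerical integration over the shared normal component.

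| ρ | Any-one error | of which favours TRT | All-three power | Power needed per test for joint 0.80 |
|---|---|---|---|---|
| 0 | 0.143 | 0.073 | 0.512 | 0.928 |
| 0.3 | 0.136 | 0.068 | 0.570 | 0.920 |
| 0.5 | 0.125 | 0.063 | 0.611 | 0.910 |
| 0.7 | 0.109 | 0.055 | 0.659 | 0.894 |

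**4. Price of an ordered procedure** (CRIES-13 first at 0.05; then Holm on the other two only if it succeeds). If each outcome alone has power 0.80, its test statistic is centred at 1.960 + 0.842 = 2.802. Power at two-sided 0.025 is Φ(2.802 − 2.241) = 0.712. At ρ = 0 the chance of claiming a given QoL outcome is 0.80 × [0.712 + (0.800 − 0.712) × 0.712] = 0.62. Simulation gives 0.65, 0.67 and 0.69 at ρ = 0.3, 0.5 and 0.7.

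**5. Components against measures.**

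| Component in Aims | Measure named |
|---|---|
| PTSD | CRIES-13 |
| Depression | none |
| Anxiety | none |
| QoL | Cantril Ladder; five-item GSE |

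**The case against.** **The hypothesis joins its parts with 'and', so alpha is not inflated.** This largely stands. The literal sense is that all must improve, or that mental health status is one construct. A reader might infer that the plan has a false-positive rate of 11–14%. The documents do not support that: the figure belongs to the any-one reading, which has the least support in the wording. But the literal reading costs joint power, and the plan does not commit to it.

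**One global test would avoid both problems.** That is correct, and the Power section mentions structural equation modelling. It does so only as a source of extra power, however. The analysis section omits it, and no composite or latent outcome is defined.

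**CRIES is evidently primary.** TRT is described as a "manualized, short term, group based intervention, which specifically focuses on" PTSD symptoms, and CRIES-8 decides entry. This is a good reason to choose CRIES-13, but it does not show that it was chosen. The same section gives self-efficacy and perceived control as the intervention's aim and presents QoL outcomes as an extension of prior designs.

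**The parent study may settle all this.** Ethical Aspects refers to a more comprehensive approved study whose protocol is not supplied. It may name a primary endpoint as well as depression and anxiety instruments. A reader might infer that these symptoms were never measured, or were measured and dropped. Neither follows; this document is simply silent. For the same reason, error rates for five outcomes would rest on scales that the document does not name, so none is given here.

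**Conclusion.** The point holds as a gap in specification that should be closed before outcome analysis. This document states one primary hypothesis over four components, supplies no primary outcome, primary wave or combining rule, and names no measure for two of the components.

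The figures show how far the readings diverge: 11–14% family-wise error under an any-one rule, against joint power of 0.51–0.66 under an all-must-improve rule. They rest on three outcomes at W2, two-sided tests at 0.05, correlations of 0 to 0.7 and a granted 0.80 per test. They ignore allocation by institution, for which no intracluster correlation is given, and they do not apply to a single global test.

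Nor should a reader infer that naming one primary endpoint secures 5% error and 0.80 power. It removes the multiplicity problem. The calibration and power of that single test under the clustered design remain whatever they are; unadjusted and two-sided, n=150 gives about 0.69 at d=0.40 even before clustering.

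**What to change.** Before outcome analysis, issue a short dated amendment that does the following.

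1. State whether outcome data by group have been seen. If they have, label the endpoint choice post hoc.
2. If the approved parent protocol already designates a primary endpoint, cite and follow it.
3. Otherwise, make CRIES-13 total at W2, intervention versus wait-list, the single primary endpoint. Make the Cantril Ladder and GSE at W2 secondary, tested with Holm only if the primary is significant. A single pre-specified global or latent-variable test at W2 is an acceptable alternative.
4. Label W3 results as lacking an untreated comparison.
5. State whether depression and anxiety were measured. If so, name the instruments and report them as secondary outcomes in the same family. Only if they were not measured, remove them from the primary hypothesis.

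**Cost.** No new data are needed. Because collection is complete, the amendment's credibility rests on item 1. Under the ordered procedure QoL becomes a secondary claim: if each outcome alone has power 0.80, the chance of claiming a given QoL outcome is about 0.62–0.69, and lower if depression and anxiety join the Holm family. The ordering itself adds no multiplicity error.
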